7.3.2.5. Feminine Product Return Rate by Visit

To quantify degree of compliance with FP collection during the randomized treatment period, the FPRR will be calculated based on the inventory of FP returned by day (dates) provided by the vendor, KCAS, the reason why the FP was not collected from the Feminine Product Collection eCFR page, and responses to the paper patient diary questions regarding bleeding experience and the use of FP obtained for the corresponding diary window (see [Table 6](#)). Specifically:

- For those who returned FP at a FP collection visit, the FPRR was calculated as the observed number of days with returned FPs (based on the inventory of FP received by KCAS) divided by the expected number of days with bleeding and use of product as reported on the patient's paper diary within the FP collection interval (as defined above).

$$\text{FPRR} = \frac{\text{observed (No. of days with returned FP [per KCAS])}}{\text{expected (No. of days reported bleeding and use of FP [per Diary])}} \times 100$$

- For those who did not return any FPs:
 - If the reason was "Amenorrheic" or "Patient only had Spotting that did not require the use of Sanitary Products" on the eCRF, their FPRR will be set to 100% because the lack of menstruation obviates the need for FP collection.
 - If the reason was "Patient failed to collect Used Products per Protocol" on the eCRF, their FPRR was set to 0.
 - If the reason was "Retreatment Visit; No Product Collection Required" or "Successful Retreatment; No Product Collection Required" on the eCRF, their FPRR was set to 0.
 - If the reason is "Other", their FPRR was set to 0.

The texts specified for reason "Other" will be reviewed by the medical team to identify those which belong to any pre-defined reasons listed in the first three bullets above and the reason will thus be treated accordingly.

7.3.3. Identifying Responder Status and Incomplete Feminine Product Collection at Each Visit

For each schedule visit, responder (MBL volume < 80 mL) status and incomplete FP collection will be identified for each patient by checking compliance with FP collection against the patient's paper diary, as measured by FPRR, and reasons for no FP collection (as displayed in Table 9).

Table 9: Identifying Incomplete Feminine Product Collection and Derivation of Responder Status at Each Visit During Randomized Treatment Period

FP Collection (Yes/No)	Reason for No FP Collection (CRF page)	Observed MBL Volume	FPRR	Incomplete FP collection	Responder Status
Yes	N/A	< 80 mL	>80-100%	Complete	Yes
	N/A	≥ 80 mL	N/A	N/A	No
	N/A	< 80 mL	≤ 80%	Incomplete, Not acceptable	Missing
No	Amenorrheic	Set as 0 mL	100%	Complete	Yes
	Patient only had spotting that did not require the use of sanitary products	Set as 4.99 mL	100%	Complete	Yes
	Patient failed to collect used products per protocol	Missing	0%	Incomplete	Missing
	Retreatment visit; No product collection required	N/A	N/A	N/A	N/A
	Successful retreatment; No product collection required	N/A	N/A	N/A	N/A
	Other	Missing	0%	Incomplete	Missing

Abbreviations: FP = feminine product; FPRR = feminine product return rate; MBL = menstrual blood loss; N/A = not available.

7.3.4. Sensitivity Analyses

To assess the robustness of the primary analysis, the following sensitivity analyses of the primary endpoint (sustained responder rate) will be conducted at Week 76.

7.3.4.1. Sensitivity Analysis 1

To assess the potential impact of the length and full exposure of the treatment, the primary endpoint (sustained responder rate) will be analyzed for the Week 76 completers population as a sensitivity analysis as appropriate. The Week 76 completers population is defined as patients in the mITT population who completed 24 weeks of treatment.

7.3.4.2. Sensitivity Analysis 2

The primary endpoint will be analyzed on the Per-Protocol population as a sensitivity analysis, using the methods specified for the primary analysis (see definition of Per-Protocol population in Section 4.2.2).

7.3.4.3. Sensitivity Analysis 3

The primary endpoint will be analyzed on the mITT population as a sensitivity analysis, using different censoring rules for some of the patients who did not have relapse during the randomized treatment period and had incomplete or missing FP collection during the randomized treatment period, which are listed below. Except the differences in the two situations listed below, the censoring rules in Table 8 will be used. The differences are:

- If patients did not have FP collection after Week 64 (ie, have ≤ 3 FP collection visits), they will be considered as having an event at the date of the first visit with incomplete or missing FP collection during the randomized treatment period.
- If patients had FP collection after Week 64 and had three or more consecutive visits with incomplete or missing FP collection, they will be considered as having an event at the date of the first visit of the three or more consecutive visits with incomplete or missing FP collection during the randomized treatment period.

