Patients were to be asked to collect FPs for alkaline hematin analysis and to return them at each visit until the analysis confirmed the return of heavy menstrual bleeding (defined as menstrual blood loss volume of ≥ 80 mL). The patients were then to be offered re-treatment with open-label relugolix +E2/NETA with the onset of the next menses. They were to continue collection of FPs for alkaline hematin analysis until two consecutive analyses confirmed resolution of heavy menstrual bleeding (menstrual blood loss of < 80 mL). Patients who experienced a return of heavy menstrual bleeding (or terminate early because they have a return of heavy menstrual bleeding) but who decline retreatment with open-label study drug were to complete an Early Termination visit and a 30-day Safety Follow-Up visit.

At the Week 104/Early Termination visit, all other patients were to have an assessment of bone mineral density (BMD) via dual-energy x-ray absorptiometry (DXA). Patients were to complete the bleeding diary daily, including compliance with study drug, vaginal bleeding, and use of FPs.

If a patient enrolls directly into another relugolix clinical study upon completion of the Week 104/Early Termination visit, then the Safety Follow-Up visit and the follow-up procedures performed under this protocol may be waived.

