4.3. Definitions, Computation, and Convention

4.3.1. Definition of Date of First Dose and Date of Last Dose of Study Drug During the Randomized Treatment Period

The randomized treatment period is the period when a patient was on one of the randomized study drugs (relugolix + E2/NETA or placebo). The date of first dose of study drug is defined as the date when a patient receives the first dose of study drug for the randomized withdrawal study following randomization. The first dose of study drug for the randomized withdrawal study was to be self-administered the next morning following the Week 52/Baseline visit.

The date of the last dose of randomized study drug is defined as the date a patient receives the last dose of randomized study drug in this randomized withdrawal study, prior to re-treatment or on the Week 104 visit date. If the complete date of last dose of study drug is unknown, the last date the study drug was known to have been taken will be used.

4.3.2. Definition of Date of First Dose and Date of Last Dose of Retreatment Drug

The date of first dose of retreatment drug is defined as the date when a patient receives the first dose of retreatment drug (open-label relugolix + E2/NETA). When the return of heavy menstrual bleeding (defined as menstrual blood loss of ≥ 80 mL) was confirmed for a patient during the randomized treatment period, the patient was to be offered retreatment with open-label relugolix + E2/NETA with the onset of the next menses.

The date of the last dose of retreatment drug is defined as the date a patient receives the last dose of retreatment drug in this randomized withdrawal study, prior to or on the Week 104 visit date. If the complete date of last dose of retreatment drug is unknown, the last date the retreatment drug was known to have been taken will be used.

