7.3. Primary Efficacy Endpoint

The primary efficacy endpoint of the study is the proportion of patients who maintained a menstrual blood loss volume of < 80 mL at Week 76 (24 weeks/EOT of the randomized treatment period) as measured by the alkaline hematin method. The primary endpoint will be referred to as sustained responder rate at Week 76 and defined as the cumulative probability of MBL volume < 80 mL measured while on randomized treatment through Week 76. For the primary analysis, primary endpoint will incorporate the censoring rules described in Section 7.3.1. The primary endpoint of sustained responder rate will be evaluated using the mITT Population.

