7.3.1.2. Censoring Rules

The censoring rules in the Kaplan-Meier method are described as the following (see Table 8):

- For patients with relapse (MBL volume ≥ 80 mL) during the randomized treatment period, they will be considered as having an event at the time of first relapse. The time of first relapse is the date of the earliest menstrual bleeding days within the first FP collection visit window in which the MBL volume is ≥ 80 mL.
- For patients who did not have relapse during the randomized treatment period and had complete FP collection at each scheduled visit during the randomized treatment period,

they will be considered as not having an event and will be censored at the last available FP collection visit date during the randomized treatment period.

- For patients who did not have relapse during the randomized treatment period and had incomplete or missing FP collection during the randomized treatment period, they will be considered as censored using the following censoring rules:
 - If patients did not have FP collection after Week 64 (ie, have up to 3 FP collection visits through Week 64), they will be censored at the date of the last available FP collection visit if there are no consecutive visits with incomplete or missing FP collection; they will be censored at the date of the last available FP collection visit prior to the consecutive visits with incomplete or missing FP collections if there are two or more consecutive visits with incomplete or missing FP collections.
 - If patients had FP collection after Week 64
 - did not have incomplete or missing FP collections at consecutive visits, they will be censored at the last available FP collection date during the randomized treatment period.
 - had two or more consecutive visits with incomplete or missing FP collections, they will be censored at the last available FP collection visit date prior to the two consecutive visits during the randomized treatment period.

The time to event or censoring will be summarized by the Kaplan-Meier method. If the event time or censoring time is after the target (Day 365), Day 365 will be used as the event time or censoring time.

A sensitivity analysis will be performed considering different censoring rules (see Section [7.3.4.3](#)).

Table 8: Censoring Rules for Kaplan-Meier Analysis During Randomized Treatment Period

Type of Patients	Event	Event Time ^a	Censored	Censoring Time ^a

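### SAP 7.3.4.1 does not say whether retreatment counts towards completing 24 weeks; read as randomized treatment, Sensitivity Analysis 1 drops most relapsers and shrinks the treatment difference

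*SAP*

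**What the plan says.** SAP 7.3.4.1 gives the aim of the analysis as "To assess the potential impact of the length and full exposure of the treatment" and defines its population, the Week 76 completers, as "patients in the mITT population who completed 24 weeks of treatment". It is to be done as appropriate. No other section defines a Week 76 completer. The disposition list in SAP 5.1 has a category for completing treatment to Week 76, but does not say which treatment.

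The endpoint is "defined as the cumulative probability of MBL volume < 80 mL measured while on randomized treatment through Week 76" (SAP 7.3), and the same section describes Week 76 as "24 weeks/EOT of the randomized treatment period". SAP 4.3.1 limits that period: "The randomized treatment period is the period when a patient was on one of the randomized study drugs". SAP 4.3.5 separately defines a cumulative period that adds retreatment.

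For women who relapse, "they will be considered as having an event at the time of first relapse" (SAP 7.3.1.2). What follows is in SAP 2.1: "The patients were then to be offered re-treatment with open-label relugolix +E2/NETA with the onset of the next menses". Women who decline have an Early Termination visit. Under Protocol 6.2, the last randomized dose is taken the day before the retreatment visit.

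**The concern.** Relapse is the event being counted, and it also takes a woman off randomized drug. If completion means 24 weeks of randomized drug, a woman who relapses early enough to be switched or to leave before Week 76 cannot be a completer. The population is then chosen largely by the outcome, and the Kaplan-Meier rate is estimated in a group from which most events have been taken out.

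The SAP recognises the mechanism elsewhere. SAP 7.1.2 withholds mixed models from the randomized period because stopping a woman's data at retreatment is informative. Restricting to completers makes the same kind of selection, here on the primary endpoint.

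Sensitivity Analysis 1 is listed as a check on the robustness of the primary result. If it attenuates the difference by construction, it cannot do that job, and a smaller difference could be misread as fragility of the primary finding.

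**Working it through.** **Inputs from the documents.** SAP 2.2: sustained responder rates of 60% (relugolix + E2/NETA) and 40% (placebo), 360 patients randomized 1:1, two-sided alpha 0.05, dropout 20%, power at least 90%. SAP 7.3.1: Week 76 is Day 169.

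**Assumption.** The delay *d* from the relapse date to the end of randomized drug. The documents give neither assay turnaround nor cycle length, so I show 0, 28 and 56 days. The delay is not zero in practice. The event is dated to the first bleeding day in the collection window (SAP 7.3.1.2), the products must then be returned and assayed, and retreatment waits for the next menses.

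**1. The plan's own figure.** n per arm = [1.96·√(2·0.5·0.5) + 1.2816·√(0.4·0.6 + 0.6·0.4)]² / 0.20² = (1.386 + 0.888)² / 0.04, about 129.3, so 130. That is 260 in total and 260/0.8 = 325 after dropout. With 180·0.8 = 144 per arm, power is 92.8%. The statement of at least 90% holds.

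**2. Completion read as randomized treatment.** A relapser stays in the set only if her switch falls after Week 76, that is, if she relapsed in the last *d* days. With a constant hazard and dropout independent of relapse, the completers' rate is

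S(169)/S(169 − d) = S(169)^(d/169),

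and the share of relapsers removed is [1 − S(169 − d)]/[1 − S(169)].

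| Delay | Placebo | Relugolix + E2/NETA | Difference | Relapsers removed (placebo, relugolix) |
|---|---|---|---|---|
| 0 days | 100% | 100% | 0 | 100%, 100% |
| 28 days | 0.4^(28/169) = 85.9% | 0.6^(28/169) = 91.9% | 6.0 points | 89%, 87% |
| 56 days | 0.4^(56/169) = 73.8% | 0.6^(56/169) = 84.4% | 10.6 points | 76%, 72% |

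**3. Simulation check** (180 per arm, 20% dropout by Day 169, 400 runs; placebo vs relugolix). With a constant hazard: 84.1% vs 90.6% for delays of 28–35 days, and 72.1% vs 83.8% for 56–63 days. With front-loaded relapse (Weibull shape 0.7): 88.2% vs 92.8% and 78.3% vs 87.3%. The difference is about 5 to 12 points throughout.

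**4. Completion read to include retreatment.** If every relapser accepts retreatment, she stays in the set with her event, and the simulation returns about 40% vs 60%, a difference of about 20 points. If a share *q* of relapsers in each arm declines and leaves before Week 76, the rate is S/[S + (1 − S)(1 − q)]. The documents give no *q*. For an assumed 20%: 0.4/0.88 = 45.5% vs 0.6/0.92 = 65.2%, a difference of 19.7 points. For 50%: 0.4/0.70 = 57.1% vs 0.6/0.80 = 75.0%, a difference of 17.9 points. Both rates rise, but the contrast changes little while *q* is the same in both arms.

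**5. The redefined population** (relapsed by Day 169, or completed 24 weeks of randomized drug), with constant hazards and 20% independent dropout by Day 169. Women who reach Day 169 without relapse or dropout: 0.8·S. Women who relapse before dropping out: [−ln S/(−ln S − ln 0.8)]·(1 − 0.8·S).
- Placebo: 0.32 and (0.916/1.139)·0.68 = 0.547. Rate 0.32/0.867 = 36.9%.
- Relugolix + E2/NETA: 0.48 and (0.511/0.734)·0.52 = 0.362. Rate 0.48/0.842 = 57.0%.
- Difference: 20.1 points.

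**The case against.** The definition says treatment, not randomized treatment, and the SAP usually adds the qualifier when it means it, as Sensitivity Analysis 3 does in SAP 7.3.4.3. The protocol synopsis describes a treatment period that may be randomized or open-label, and Protocol 4.5 defines study completion by the Week 104 visit, which a retreated woman can reach. On that reading a retreated relapser is a completer and keeps her event. This stands as a possible reading, so the starting point is an undefined population and not a proven bias. It does not settle the matter. A placebo woman moved to open-label relugolix has not had full exposure to her assigned treatment, which is what the analysis says it examines, and relapsers who decline retreatment are still lost.

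A reader might go further and infer that both arms would show 100%, with no difference left. The documents do not support that. It needs an immediate switch at relapse, whereas randomized drug continues until the day before the retreatment visit at the next menses. Under the constant-hazard delays in the table, 11% to 28% of relapsers remain in the set.

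It is also fair that the proposed population is not neutral. It keeps every relapse while removing non-relapsing early discontinuers, so both rates fall by about 3 points, and it includes relapsers who did not have 24 weeks of randomized drug. The cost is small and the contrast is preserved.

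Finally, this is one of three sensitivity analyses, outside the testing sequence, and Sensitivity Analysis 3 keeps the full mITT population. That limits the consequence but does not supply the missing definition.

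**Conclusion.** The point holds as one of definition with a quantifiable consequence. On the natural reading, Sensitivity Analysis 1 selects on the endpoint event and would show roughly 6 to 11 points where the true difference is 20. This rests on the planning rates being true, a constant relapse hazard, dropout independent of relapse and an assumed delay of 28 to 56 days; front-loaded relapse in the simulation lowers the bottom of the range to about 5 points. On the retreatment-inclusive reading, the loss is confined to relapsers who decline retreatment and leave before Week 76.

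A reader might infer that the trial's main conclusion is at risk. It is not: the primary analysis, the alpha allocation and the power do not depend on this population, and because the bias shrinks the difference it does not favour the drug. The change should be made so that the analysis can serve as a robustness check, and the choice of population should not be left open until after unblinding.

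**What to change.** Replace the definition in SAP 7.3.4.1 with one that does not depend on being event-free: the Week 76 completers are mITT women who either had a relapse event (MBL of 80 mL or more) on randomized treatment by Week 76 (Day 169), or completed 24 weeks of randomized treatment. Only women who stopped randomized drug early without relapsing are then left out.

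Add that the analysis is supportive only, and that leaving out these women slightly lowers both rates (about 57% vs 37% instead of 60% vs 40% under 20% independent dropout). Adjust the stated aim to match, since early relapsers in this set did not have full exposure.

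The cost is one redefined sentence and a short note in the SAP. No data collection, clinical rule, primary analysis or sample size changes.

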7.3.5. Subgroup Analyses

Subgroup analyses of the primary efficacy endpoint of sustained responder rate comparing relugolix+E2/NETA and placebo will be performed to determine whether treatment effect is consistent across clinically meaningful subgroups. The differences in sustained responder rate and corresponding 95% CIs (calculated via linear transformation of the difference in relapse free survival function with pooled variance) will be displayed in a forest plot. Subgroups will include but not be limited to the following: baseline MBL volume in the pivotal study (< 225 mL vs. ≥ 225 mL), geographic region (North America vs. Other), duration of exposure to relugolix prior to randomization (28 weeks vs. 52 weeks) as well as other baseline subgroups such as age, and race. Details are provided in Table 10.

Table 10: Planned Subgroup Analyses

Subgroup Name	Subgroup Level
Geographic region	North America vs. Other
Menstrual blood loss volume at Pivotal Baseline (mL)	< 225 vs. \geq 225 < 120, 120 to < 160, 160 to < 225, \geq 225
Duration of exposure to relugolix prior to randomization (weeks)	28 vs. 52
Age category (years) at Pivotal Baseline	< 40 vs. \geq 40
Race	Black or African American vs. Other ; Black or African American, White, Other
Volume of myoma at Pivotal Baseline (cm ³)	< 25 vs. \geq 25
Volume of uterus at Pivotal Baseline (cm ³)	< 300 vs. \geq 300
BMI (kg/m ²) at Pivotal Baseline	< 30 vs. \geq 30 < 25, 25 to < 30, 30 to < 35, 35 to <40, \geq 40
Maximum NRS score for uterine fibroid-associated pain at Pivotal Baseline	< 4 vs. \geq 4

Abbreviations: BMI = body mass index; NRS = Numerical Rating Scale.

7.4. Secondary Efficacy Endpoints

Comparative statistics (p values, 95% CIs for differences) will be provided for treatment comparison of the relugolix group with the placebo group for secondary efficacy endpoints during randomized treatment period.

7.4.1. Key Secondary Endpoints

For testing whether relugolix+E2/NETA is statistically significantly superior to placebo for the primary efficacy endpoint as well as the three key secondary endpoints listed below, a fixed sequence testing procedure will be applied to maintain the family wise type I error rate. Under this testing procedure, the primary endpoint will be tested first at a 2-sided 0.05 significance level. If the p value for primary endpoint is < 0.05, the three key endpoints will be tested sequentially in the order depicted in [Figure 1](#).

[figure not shown]
Figure 1: Fixed Sequence Testing Procedure for Primary and Key Secondary Endpoints

Primary Endpoint

- Sustained responder rate at Week 76

Key Secondary Endpoints

- Time to relapse (MBL \geq 80mL)
- Sustained responder rate at Week 104
- Amenorrhea rate at Week 76 / EOT

Abbreviations: EOT = end of treatment; MBL = menstrual blood loss.

7.4.1.1. Time to Relapse (Menstrual Blood Loss Volume \geq 80 mL)

For the endpoint of time to MBL volume \geq 80 mL (event) during the randomized treatment period, time-to-event will be defined as weeks from first dose of the randomized withdrawal study drug to first occurrence of MBL volume of \geq 80 mL. The corresponding menstruation start date will be considered as the event date. Patients without an event will be censored by following the same censoring rules described in Section 7.3.1.2. Kaplan-Meier methods will be used to describe the time to event (relapse) distributions for each study treatment group from which median time to event will be derived. Hazard ratio (95%CI) of relugolix + E2/NETA to placebo for risk of relapse (MBL volume \geq 80mL) will be provided using a proportional hazard model stratified by the stratification factors (pivotal study baseline MBL volume (< 225 ml vs. \geq 225 mL) and duration of exposure to relugolix (28 weeks vs. 52 weeks). p-value for comparison of relugolix + E2/NETA to placebo based on the stratified log-rank test will be provided.

7.4.1.2. Proportion of Patients Who Maintained a Menstrual Blood Loss Volume of < 80 mL at Week 104

The proportion of patients who maintained a menstrual blood loss volume of < 80 mL by Week 104 (52 weeks of the randomized treatment period) as measured by the alkaline hematin method will be analyzed using the same method as that for primary efficacy endpoint described in Section 7.3. It is noted that sustained responder rate at Week 104 (Day 365) will be defined as the KM estimates from the same KM curves and will be analyzed using the same method as for the primary endpoint (see Section 7.3.1).

No subgroup analysis will be performed for this secondary efficacy endpoint.

The proportion of patients who maintained a menstrual blood loss volume of < 80 mL will also be summarized during the cumulative treatment period (including both randomized treatment period and the retreatment period).

The proportion of patients who had a menstrual blood loss volume of < 80 mL at a visit will also be summarized descriptively by visit during the cumulative treatment period (including both randomized treatment period and the retreatment period).

